5.6.1 Vulnerable Population

The study will include vulnerable populations as research participants. Adult research participants (birthing persons) may be the persons with Limited English Proficiency (LEP), illiterate persons, unable to read and write, or visually impaired, or deaf persons.

Enrollment of the research participants will be provided at the Los Angeles County Area - one of the most culturally and ethnically diverse cities in the US. The likelihood of encountering eligible participants with limited English proficiency is high. With respect to the cultural and ethnic diversity of Los Angeles population, recruitment of the LEP and / or illiterate birthing persons will be arranged according to the UCLA OHRP Guidance "Research Involving Non-English Speaking Research Participants (May 9, 2019)".

In case of LEP, the informed consent process will be conducted using the services of the qualified interpreters using one of the two available consent methods: Preferred Method or Short-Form Method.

For Spanish research subjects, the **Preferred Method** of enrollment of the non-English speaking research participants will be used. After IRB approval of the ICF English version, this form will be translated by qualified translator into the Spanish language, send to the IRB as an amendment for reviewing and subsequent approval. The IRB approval of the Spanish ICF version should be obtained by the research team before enrollment of the Spanish birthing persons with LEP. Potential study participants will be given the opportunity to review the ICFs in Spanish. Additionally, the PI, or the member of the research team, or qualified interpreter, who speaks Spanish and English, will be available during the study to answer questions and conduct the project. If Spanish speaking patient decides to participate in the research, the patient prints, signs, and dates the ICF. Then person conducting consent process, also prints, signs, dates ICF, and provides the copy of the ICF to the birthing person.

For the occasional and unexpected enrollment of the **non-Spanish research subjects** with LEP, the **Short Form Method** may be implemented during enrollment. The UCLA

OHRP documents: “Checklist for Using the “Short Form” Method of Consent for Non-English Speaking Research Participants (February 20, 2020)” and “Research Participant Bill of Rights/ Experimental Subjects Bill of Rights (July 12, 2021)” (Bill of Rights) will be used to assure all UCLA IRB requirements are met.

The Short Form Method is appropriate for enrollment the participants under certain circumstances:

- The patient wants to be study participant and is otherwise eligible, but did not speak English or Spanish;
- the PI has not sufficient time to translate the ICF and obtain the IRB approval before planned date of the participant’s enrollment;
- the research project is the minimal risk study;
- the study has a short window to enroll the birthing person.

The Short Form informed consent procedure will be as follows:

- The study personnel upload from the UCLA OHRP website the Bill of Rights on the birthing person’s native language, or language, that the patient is fluent in.
- If the UCLA OHRP website does not contain the Bill of Rights on the necessary language, and the PI would like to enroll the patient, the study personnel arrange the professional/ certified translation of the Bill of Rights into the patient’s language.
- The statement “The elements of consent from the consent form were presented orally” is added to the translated Bill of Rights.
- Lines for the participant’s printed first and last names, signature, and date are added to the Bill of Rights.
- Lines for the PI/ designee’s printed first and last names, title, signature, and date are added to the Bill of Rights.
- Lines for the Interpreter/ Witness’s printed first, and last names, signature, and date are added to the Bill of Rights.
- The PI secures the qualified interpreter who speaks both English and the birthing’s person language to obtain, document and sign the consent documents.
- The PI/ designee explains the research to the birthing person, using Patient-Centered approach, answers questions, and assess participant’s comprehension of the study.
- Study participant prints first name and last name on the translated Bill of Rights, signs, and dates the document.
- Study participant prints first name and last name on the English version of the ICF, signs, and dates the document.
- After consenting, the PI gives the copy of the signed Bill of Rights and English version of the ICF to the birthing person.
- The researcher documents all details of the informed consent process in the research document.
- Within 30 days after consenting, the study personnel arrange translation of the ICF from the English to the participants own language, that is the language used during Short Form Method.
- The PI/ designee submits the Post Approval Incident Report to the UCLA IRB, notifying them of about implementation of the Short Form Method for enrollment the birthing person into the Perinatal Repository Protocol. The amendment should be submitted to the IRB

along with the translated ICF and copy of the Bill of Rights. The PI provides the IRB with the description of the plan, including timing, to provide the full translated ICF to the study participant.

- After obtaining the IRB approval of the translated ICF, the PI provide the birthing person with the translated ICF in person during visit or by mail/ email. All details are recorded by study personnel in the research records.
- At the time of the Continuing Review, the PI summarizes any and all uses of the Short Form Method.
- During the participant's visits, the PI, or the member of the research team, or qualified interpreter, who speaks the target subject population will be available to answer questions and conduct the project.

A special approach will also be applied to ***visually impaired persons*** and ***illiterate*** persons who understand English. The ICF will be read aloud, explained, and checked by the PI / designee for comprehension.

For consenting ***deaf participant***, the PI will use deaf service available through the UCLA Health System Interpreter/ Translation and Deaf Services program.

By answering and asking questions, the PI/ designee determines whether the potential participant comprehends the consent information to ensure the informed consent is valid. An impartial third-party witness will confirm the informed consent process has taken place. Both the PI and the witness will sign and date the ICF. The copy of the ICF will be provided to the research participant.

5.6.2 Additional Protection for Pregnant Birthing Person and Neonate/ Fetus

According to 45 CFR 46: Protection of Human Subjects under United States Law (1974), the additional protections for pregnant birthing persons, neonates, and fetuses are provided in the Protocol. Additional protection of Repository participants will be arranged according to the UCLA OHRP Guidance: "Special Populations – Pregnant Women, Fetuses, Neonates or In Vitro Fertilization" and "Chart for Regulatory Requirements for Pregnant Women, Fetuses and Neonates".

The Repository does not imply direct benefits to the birthing person, both the birthing person and the fetus/ neonate. Risk for the study participant is minimal.

The research participants will be recruited during perinatal visits. The birthing persons may also be recruited and consented while they are in early labor (infrequent contractions (less than 3 per minute) and cervix < 4 cm).

The study will not recruit and seek to consent research participant under the following conditions:

- birthing person is in active labor: contractions every 3-4 minutes, cervix > 4 cm;
- birthing person is distracted, exhausted, and in a degree of pain or discomfort that could preclude valid consent;
- patient is sedated.

Results of the Protocol implementation make the substantial scientific contribution to the prevention of the non-favorable clinical outcome for high-risk pregnancy. Creation of the Perinatal Repository address an important clinical issue. It is necessary postulate that the

birthing person will not be provided inducements like money to terminate the pregnancy. The PI and co-PIs do not have part in determining the viability of the fetus. Postpartum, no research tests of infants for research purposes will be performed. Repository Material records clinical data on the newborns condition. The research will not terminate the functioning of the heart and respiration of the nonviable neonate. After delivery, the viable neonates are protected by the protections allotted to normal study participants and the additional protections of children.

Therefore, there is no added risk to the fetus/ neonate and the birthing person. . Intention to collect perinatal data is aiding the efficiency and effectiveness of de-identified biorepository for pregnancy at risk outcome research. The results of the study are important and cannot be obtained through other means.

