5.4.2 Standard of Care

Screening and enrollment of study participants will be organized on the labor and delivery units at both Ronald Reagan Medical Center and Santa Monica Hospital. High-professional physicians, nurses, midwives, and staff of the Department of Obstetrics and Gynecology represent the nationally and internationally recognized leaders in the delivery of women's medical care. The provision of patient care is carried out in accordance with the strict standards of medical care implementation at the David Geffen School of Medicine at UCLA.

Whatever the birthing person does consent / or does not consent the participation in the study, it will not change the person's labor management.

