5.6 Informed Consent

Informed consent process should be performed by the PI/ designee in accordance with the UCLA OHRP Guidance "Obtaining and Documenting Informed Consent (March 2, 2021)". Consenting will be arranged in the private room in non-emergency or emergency setting of the UCLA Health. Signed and dated ICF will be obtained from the research participant. Prospective study participants will be provided with sufficient opportunity to consider whether or not to participate in the study:

- The PI/ designee meets the prospective participants/ families to review the ICF and provide an oral explanation of the study. Individuals will be given a chance to ask questions before making a considered decision about taking a part in the study.

- Prospective study participants/ families will have the opportunity to take the ICF home and discuss the documents with others prior to making decision.

- The persons will be given unlimited time until childbirth to decide whether they wish to participate in the study.

Investigator or study team member will evaluate person's comprehension of the information conveyed during the consent process. The PI/ designee provides initial assessment of patient's capacity to consent through routine interactions with the potential study participant.

The PI should ensure that the patient understands the following information:

- Writing the ICF means enrollment the persons as the research participant to the study "The UCLA Perinatal Biospecimen Repository".

- Participation in research is completely voluntarily. The birthing person may agree to participate in the study or disagree to participate without any negative consequences. The research participant has the right at any time to refuse to participate in the project without explanation and withdraw the consent.

- Participation in the Protocol means donation of patient's biospecimens and clinical data to the study team.

- Protocol-specific procedures will take place according to the Schedule of events.

The Perinatal Repository is a non-interventional minimal risk study without direct benefits to the birthing persons and their neonates/ fetuses.

- Research participants receive copy of the signed ICF with contacts of the [name]'s Lab and UCLA OHRP. If the participants have questions about the study or experiences problems or changes their opinion regarding participation, they can reach out to the investigator or UCLA Research Administration using that information.

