5.9 Ethical Considerations

Under implementation of this Protocol, the researchers plan to conduct study specifically involving following populations/ specimens:

1. Pregnant birthing persons/ fetuses.
2. Adults who are competent to give written informed consent.
3. Participants unable to read, speak, and/ or understand English.
4. Fetal tissue.
5. Neonates (clinical data only).

Inclusion of the vulnerable patient populations is necessary to achieve the purpose the study and implement the objectives of the research project. Additional safeguards are developed to protect this population from coercion, undue influence, and exploitation. The PI/ designee will provide assessment of capacity to consent for the birthing person as the primary additional safeguard measure. If upon assessment the potential participant will be found as person unable to give informed consent, or person with diminished capacity to consent, the PI/ designee will not seek surrogate consent for their participation in the Perinatal Repository Protocol.

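### Section 5.6.2 sets the early-labor contraction limit for seeking consent at 3 per minute, 9 to 12 times the protocol's own active-labor rate; this is very probably a unit error

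*Protocol*

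**What the plan says.** Section 5.6.2 of the Protocol sets the rules for approaching people in labor. Recruitment is to take place during perinatal visits, and consent may additionally be sought in "early labor (infrequent contractions (less than 3 per minute) and cervix < 4 cm". A list of three conditions then rules consent out:

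- The first condition concerns the stage of labor: "birthing person is in active labor: contractions every 3-4 minutes, cervix > 4 cm".
- The second condition concerns how the person is coping: "birthing person is distracted, exhausted, and in a degree of pain or discomfort that could preclude valid consent".
- The third condition concerns medication: "patient is sedated".

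Section 5.6.2 of the combined protocol and SAP carries the same contraction and cervix figures. No other section of either document gives a contraction limit.

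Two other sections bear on how often the rule could be used. Section 5.4.2 states that "Screening and enrollment of study participants will be organized on the labor and delivery units". On the time allowed for the decision, section 5.6 states: "The persons will be given unlimited time until childbirth to decide whether they wish to participate in the study".

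**The concern.** The limit contradicts its own description. Contractions just under 3 per minute are not infrequent, and they come far faster than the rate the same section uses to define active labor. The early-labor test is meant to have two working parts, contraction frequency and cervical dilation. As written, the frequency part removes no one contracting at the active-labor rate, so only the cervix value does any work there.

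This is an operative threshold for when consent may be sought, in the section that sets out additional protection for pregnant participants. Enrollment is placed on labor and delivery units and the decision window runs to childbirth, so consent in labor is foreseeable. What is at stake is whether an objective limit on consent in labor works as written, without staff having to guess the unit.

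**Working it through.** **Inputs**, all from section 5.6.2 and identical in both documents:

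- Early-labor limit: fewer than 3 contractions per minute, jointly with cervix below 4 cm.
- Active-labor description: one contraction every 3 to 4 minutes, cervix above 4 cm.

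The limit is stated, not derived, so there is no calculation in the plan to reproduce. The check is a unit conversion.

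**Step 1. Common units** (interval = 60 s / rate per minute; rate = 1 / interval in minutes).

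- Early-labor limit: 60 / 3 = 20 s between contractions.
- Active labor, every 3 min: 180 s, or 1/3 = 0.333 per minute.
- Active labor, every 4 min: 240 s, or 1/4 = 0.250 per minute.

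**Step 2. Ratio of the limit to the active-labor rate.**

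- 180 / 20 = 9
- 240 / 20 = 12

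Both active-labor rates lie well below 3 per minute, so both pass the contraction part of the early-labor test.

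**Step 3. Two test cases.**

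| Case | Early-labor sentence | Active-labor bullet, comma read as *and* | Comma read as *or* |
|---|---|---|---|
| Every 3.5 min (0.286/min), cervix 3 cm | Permitted: 0.286 < 3 and 3 < 4 | Not barred: 3 is not > 4 | Barred |
| Every 3.5 min, cervix 5 cm | Not permitted: 5 is not < 4 | Barred | Barred |

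The gap is therefore confined to people with cervix below 4 cm who contract at the active-labor rate or faster. For someone contracting every 3 to 4 minutes, it opens fully if the comma means *and*. If it means *or*, the sentence and the bullet contradict each other.

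**Step 4. Candidate corrections.** The table shows the share of the 3-to-4-minute band that each limit would still admit. This is a share of a one-minute range of intervals, not of people.

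| Limit | Interval required | Share of band admitted |
|---|---|---|
| Under 3 per minute (as written) | > 0.333 min | (4 − 3) / (4 − 3) = 100% |
| Under 3 per 10 minutes | > 10/3 = 3.333 min | (4 − 3.333) / (4 − 3) = 67% |
| More than 4 minutes apart | > 4 min | 0% |

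Changing the unit to 10 minutes makes the figure plausible, but it still overlaps the active-labor band between 3.33 and 4 minutes.

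**The case against.** The strongest reply is that little turns on the slip in practice. Dilation separates the two states on its own, below 4 cm against above 4 cm. If the comma means *or*, the person in the first test case is barred whatever the early-labor limit says. If it means *and*, that person is not in active labor by the protocol's definition, and allowing consent may be intended. A clinician would take the word infrequent as the guide and would hardly apply it to contractions 20 seconds apart. Labor is also only an extra route, since section 5.5 has a physician making contact during visits. The other protections do not depend on contraction rate: the pain, distraction or exhaustion bar, the sedation bar, the investigator or designee who "provides initial assessment of patient's capacity to consent through routine interactions" (section 5.6), and the "assessment of capacity to consent for the birthing person as the primary additional safeguard measure" (section 5.9).

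Most of this stands, and it is why the point is minor. It does not make the figure right. Those other protections rest largely on judgment and do not replace a numeric limit that fails as written. The protocol also does not say which reading of the comma applies.

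Two objections to the remedy have some force. The intended unit cannot be recovered from the documents, and nothing in them requires the two contraction ranges to be disjoint, so any replacement value is a proposal. A non-overlapping limit could also leave someone with cervix below 4 cm contracting every 3 to 4 minutes neither permitted nor barred, if the comma means *and*. The conjunction therefore has to be settled in the same edit.

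**Conclusion.** The limit is wrong as written. It stands at 9 to 12 times the protocol's own active-labor rate, contradicts the adjective attached to it, and is corrected nowhere else. That it is a unit error is an inference, but a strong one. Both documents carry the same figures, so this is not a text-extraction fault.

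Severity is minor. The conclusion covers this one limit and the unclear comma. A person who meets the full active-labor description is still barred, and the remaining safeguards are intact. The documents give no count of people approached in labor, so the number affected cannot be computed. No sample size, estimate or analysis changes.

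**What to change.** In section 5.6.2 of both documents (or of the current one only, if the other has been superseded):

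1. Restate the early-labor limit as an interval that does not overlap the active-labor band, for example contractions more than 4 minutes apart together with cervix below 4 cm. Changing the unit to 10 minutes is not enough if overlap is to be avoided.
2. State whether the two active-labor criteria are joined by *and* or by *or*. If *and* is chosen, also say whether someone who fits neither description may be approached.

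The cervix values, the pain, distraction or exhaustion bar, the sedation bar and the capacity assessment can stay as they are. The investigators and the IRB should confirm the final values.

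The cost is one phrase and one conjunction per document, a clarifying sentence if *and* is chosen, and possibly a few fewer people approached in labor.

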5.7 Payment to Participant/ Families

There is no financial incentive foreseen in this study. No payment will be provided to the participants/ families.

5.8 Confidentiality

All study Materials, data and records generated per this protocol will be kept confidential in accordance with UCLA Health policies and guidance. Special HIPAA compliance activities for this study are outlined above. The PI and the study personnel will not use biospecimens and linked clinical data for any purpose other than conducting the study per protocol.

The safeguards to maintain participant's privacy and confidentiality are described above. To ensure compliance with the HIPAA requirements, separate measures have been developed in case the PI moves to another university, as well as in case of the future dissemination of the scientific institutions and organizations. The additional safeguard measures are set forth under Data Collection and Management section.

5.9 Ethical Considerations

Under implementation of this Protocol, the researchers plan to conduct study specifically involving following populations/ specimens:

1. Pregnant birthing persons/ fetuses.
2. Adults who are competent to give written informed consent.
3. Participants unable to read, speak, and/ or understand English.
4. Fetal tissue.
5. Neonates (clinical data only).

Inclusion of the vulnerable patient populations is necessary to achieve the purpose the study and implement the objectives of the research project. Additional safeguards are developed to protect this population from coercion, undue influence, and exploitation. The PI/ designee will provide assessment of capacity to consent for the birthing person as the primary additional safeguard measure. If upon assessment the potential participant will be found as person unable to give informed consent, or person with diminished capacity to consent, the PI/ designee will not seek surrogate consent for their participation in the Perinatal Repository Protocol.

6 SAFETY MANAGEMENT

The Perinatal Repository is a minimal risk study.

6.1 Clinical Adverse Events

Unanticipated problems involving risks to subjects and others will be monitored throughout the study according to the UCLA OHRP Guidance “Decision Tree: Adverse Events (February 20, 2021)”.

6.2 Adverse Event Reporting

Since the study procedures are not greater than minimal risk, SAEs are not expected. If any unanticipated problems related to the research involving risks to subjects or others happen during the course of this study these will be reported to the IRB in accordance with UCLA IRB Guidance and Procedure: Post-Approval Reporting Requirements (PAR) for Investigators: Reporting of Unanticipated Problems, Including Adverse Events as well as Protocol Violations, Deviations and Incidents and the Reporting of Updated Study Safety Information.

7 PUBLICATION POLICY

The PI reserves the right to make public presentation of the scientific data in any way related to this clinical study. Study participants' identifiers will not be used in public presentation.

Acquaintance of the scientific community with research data can be carried out in the form of research publications, articles, reviews, abstracts at research congresses, oral / video presentations, reports, press releases, publication of information about the research on the Internet and in other ways, opted by a discrete PI decision.

Public presentation of the research material may be implemented during the preparation of this clinical study, throughout the conducting of the study, and upon completion of the study for an unlimited period of time.

The PI should assure that the actual information relating to the study will be publicly available on the Internet at the website www.clinicaltrials.gov.

The inclusion of illustrative cases in the presentation of study is not intended. If, in the future, during the implementation of the research project, special circumstances arise that may result in disclosure of identifiable information, or may create opportunities for such disclosure, the PI will promptly notify the IRB in writing. Study presentation approval should not be withheld unreasonably.

In case of a difference of opinion regarding the data reported and publication, the PI will contact the UCLA Office of Research Administration for a prompt review and a decision that satisfies all concerned parties.

Any scientific work designed and generated in connection with this protocol will be the intellectual property of the PI / [name]'s Lab as author and owner of copyright for such document.

